2. PHARMACOKINETIC, AND IMMUNOGENICITY ANALYSES

2.1 PHARMACOKINETIC ANALYSES

2.1.1 Available data

Blood samples will be collected for the determination of CHF10067 in serum at the following time points: pre-dose (within 75 minutes from start of infusion), at the end of infusion, and 2, 4, 8, and 20 hours after the end of the infusion and 5, 7, 14, 28, 56 and 84 days post-dose.

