2.1.2 Endpoints and derivation rules

The following PK parameters will be derived for serum CHF10067:

- AUC_{0-t} , AUC_{inf} , C_{max} , t_{max} , C_{inf} , t_{inf} , CL , V_z , $t_{1/2}$.

Standard non-compartmental methods will be used for the calculation of the PK parameters from the individual serum concentration – time profiles using actual sampling time points from start of infusion. If actual sampling time is not available, nominal time will be used (see also section 6.1.3.1). The analysis will consider time only in hours and minutes. Any seconds in the time part of a record will be imputed by zero. The area under the serum concentration-time curve (AUC) will be calculated according to the linear trapezoidal method.

PK parameters definition

- AUC_{0-t} : AUC from 0 to the last quantifiable concentration;
- AUC_{inf} : AUC from 0 to infinite time calculated as: AUC extrapolated to infinity will be calculated as the sum of AUC_{0-t} and a residual part extrapolated to infinite time. The residual area from the last concentration data point to infinite time is calculated using the approximation:

$$\int_t^{\infty} C_t dt = C_t / \lambda_z$$

where λ_z is the first order terminal rate constant, estimated by linear regression of the terminal loglinear segment of the plasma log concentration curve, and C_t is the last quantifiable concentration data point;

- C_{max} and t_{max} : the value and time of the maximum serum concentration will be obtained directly from the experimental data without interpolation;
- C_{inf} and t_{inf} : the value and time of the serum concentration at end of infusion;
- CL : clearance will be calculated as:

$$Dose / AUC_{inf}$$

- V_z : volume of distribution will be calculated as:

$$Dose / (\lambda_z * AUC_{inf})$$

	Statistical Analysis Plan	
CLI-10067AA1-01	Final Analysis	Final 1.0 of 30MAY2024

- $t_{1/2}$: terminal half-life, associated with negative slope ($-\lambda z$), will be calculated as $0.693/\lambda z$ from the individual drug concentration time profiles

Criteria for $t_{1/2}$ estimation

- At least three time points (excluding t_{max}) should be used for the determination of the elimination rate constant (λz), otherwise the $t_{1/2}$ as well as the derived parameters (AUC_{inf} , CL and Vz) cannot be estimated and will be presented as “NE” (not estimated) in the tables.

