6.1.3.1 EXCLUSION OF DATA FROM PK ANALYSIS

Subjects and/or PK data can be excluded from the PK set or PK analysis based on the important protocol deviations with potential impact on PK. Below, the rules for handling PK assessments not performed, or performed out of the allowed window, or not reportable are described. In addition to the important protocol deviations, PK data can be excluded based on specific rules after disclosure of the bioanalytical data or specific criteria for PK parameters. The criteria of the latter are described in section 2.1.2.

Important protocol deviations

The impact of PK assessments not performed, or performed out of the allowed window, or not reportable will depend on the number of deviations per profile and the timing of the deviation:

At predose

The impact of serum PK assessments performed out of allowed window or taken after start of infusion will be evaluated during the DRM.

For serum PK assessments not performed or not reportable at pre-dose, see section 6.3.1 for proper imputation rules for PK parameter estimation.

At t_{max}

For serum PK assessments not performed, or performed out of allowed window, or not reportable at the expected t_{max} , the general rule is the following: the resulting estimation of C_{max} , t_{max} and AUCs could not be accurately determined, and these parameters will be excluded from PK analyses. This deviation will have no impact on the estimation of $t_{1/2}$. The expected t_{max} of CHF10067 is within 1 hour from the end of infusion.

At t_{inf}

[figure not shown]
For serum PK assessments not performed, or performed out of allowed window, or not reportable at the expected t_{inf} , the general rule is the following: the resulting estimation of C_{inf} could not be accurately determined, and this parameters will be excluded from PK analyses. This deviation will have no impact on the estimation of $t_{1/2}$.

At last planned sampling time point

For serum PK assessments performed out of allowed window at the last planned sampling time point, in order to minimise the risk to under- or overestimate AUC_{0-t} , AUC_{0-t} will be calculated using the theoretical time of the last planned timepoint instead of the actual time. Note that in case the last sample is taken before the planned sampling time point, this AUC_{0-t} can only be estimated if λz is reliably measurable.

		Statistical Analysis Plan	
CLI-10067AA1-01	Final Analysis	Final 1.0 of 30MAY2024	

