For serum PK assessments not performed or not reportable at the last planned sampling time point, the following schema will be used to determine the handling of impacted AUCs (C_x , C_y and C_z are adjacent concentration samples at the end of the profile, with $t_x < t_y < t_z$; thus t_z being the last planned sampling time point of the profile):

Multiple missing PK assessments

The impact of multiple PK assessments not performed or not reportable, i.e., at least 2 adjacent intermediate values are missing, or more than 3 intermediate values are missing, the PK profiles will be discussed case by case in the DRR and/or PK DRR. If 1, or 2 non adjacent intermediate values are missing, no impact on PK parameter estimation is expected.

Two serum samples at the same actual time

The Phoenix WNL software cannot handle two identical actual sampling time points in a profile. Therefore, if two serum samples are taken at the same time, the sample taken closest to the planned sampling time point will be used while the other will be excluded from PK parameter estimation.

Rules after disclosure of the bioanalytical data

After disclosure of the bioanalytical data, subjects and/or PK data will not be excluded based on post-hoc statistical analysis or for pharmacokinetic reasons, except for certain cases described below (in line with the EMA guideline on the investigation of bioequivalence CPMP/EWP/QWP/1401/98 Rev.1 2010).

All BLQ values

When plasma concentrations are BLQ at all time points, no PK parameters will be estimated and the subject will be excluded from the PK set.

Non-zero baseline concentration > 5% of C_{max}

Statistical Analysis Plan

CLI-10067AA1-01

Final Analysis

Final 1.0 of 30MAY2024

Subjects with Day 1 pre-dose values exceeding 5% of the C_{max} will be excluded from the PK set.

AUC_{0-t} lower than 5% of the corresponding geometric mean AUC_{0-t}

Subjects with an AUC_{0-t} lower than 5% of the corresponding geometric mean AUC_{0-t} (calculated without inclusion of data from the outlying subject) will be excluded from the PK set.

Abnormal PK concentrations or profiles

Abnormal PK concentrations or profiles will be discussed case by case in the PK DRR.

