6.3 IMPUTATION AND ROUNDING RULES

6.3.1 *Missing values*

No imputation of missing values will be done (i.e., observed cases analysis), except missing pre-dose concentrations will be imputed per rules below for PK parameter derivation only:

- The missing pre-dose PK concentration will be set to 0 for PK parameter derivation.

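### SAP 6.1.3.1 treats one or two non-adjacent missing intermediate PK samples as harmless; with linear trapezoids this fails for Days 28 and 56 (and Day 14 if the half-life is short), mainly for individual AUC and CL

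*SAP*

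**What the plan says.** SAP 2.1.1 plans one serum sample before dosing and one as the infusion stops; the remaining times are "2, 4, 8, and 20 hours after the end of the infusion and 5, 7, 14, 28, 56 and 84 days post-dose". SAP 2.1.2 fixes the integration: "The area under the serum concentration-time curve (AUC) will be calculated according to the linear trapezoidal method". SAP 6.3.1 imputes no missing concentration other than the pre-dose one, so the trapezoid spans any gap.

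SAP 6.1.3.1 opens by saying that the impact of a missing sample depends on both the number of deviations and their timing. For intermediate samples it then uses only number and adjacency. Case-by-case review is triggered when "at least 2 adjacent intermediate values are missing, or more than 3 intermediate values are missing". Otherwise: "If 1, or 2 non adjacent intermediate values are missing, no impact on PK parameter estimation is expected". For a missing sample at the expected t_max, by contrast, it says that "AUCs could not be accurately determined, and these parameters will be excluded from PK analyses".

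Under SAP 2.1.4 a missing sample appears as NS in the sampling-time table and NRS in the concentration table. SAP 2.1.2 provides for marking PK data that are excluded from the analysis; it provides no mark for an AUC computed across a gap.

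**The concern.** The intermediate samples differ greatly in how much of the AUC depends on them. Those from 2 h to 20 h are hours apart on a slowly falling curve, so losing one changes almost nothing. Days 14, 28, 56 and 84 are 14 to 28 days apart. Without Day 28, a straight line joins Day 14 to Day 56 (42 days); without Day 56, it joins Day 28 to Day 84 (56 days). A straight line lies above an exponential decline, so the area is overstated, and CL and Vz, which divide by AUCinf, are understated.

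At stake are individual AUC and CL values. They are tabulated with six active subjects per dose, and Listing 16.2.6.1 sets AUC and clearance beside ADA titre for each ADA-positive subject. An inflated AUC there could hide faster clearance in a subject for whom that is the question.

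**Working it through.** **Inputs from the documents.** Target times after end of infusion (SAP 6.2.4): 0, 2, 4, 8, 20 h, then 96, 144, 312, 648, 1320, 1992 h, so that Days 14, 28, 56 and 84 are 13, 27, 55 and 83 days. Linear trapezoid; AUCinf = AUC0-t + C_t/λz; CL = Dose/AUCinf.

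**Assumptions not in the documents.** Half-life 7, 14, 21 or 28 days; infusion 1.5 h; mono-exponential decline; no assay noise; quantifiable to Day 84.

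**The plan's own figure.** It is qualitative: no impact, so about 0%.

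**Worked case, half-life 14 days** (level 1 at end of infusion, time in days, infusion phase ignored). C(t) = 2^(−t/14) gives C(13) = 0.5254, C(27) = 0.2627, C(55) = 0.0657, C(83) = 0.0164. Complete AUC0-t = 20.90.

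- Day 28 missing: bridge (0.5254 + 0.0657)/2 × 42 = 12.41, replacing 5.52 + 4.60 = 10.11. Excess 2.30; 2.30/20.90 = +11.0%.
- Day 56 missing: bridge (0.2627 + 0.0164)/2 × 56 = 7.82, replacing 4.60 + 1.15 = 5.75. Excess 2.07; 2.07/20.90 = +9.9%.

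**All cases: change in AUC0-t against the same profile with every sample (%)**

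| Missing | 7 d | 14 d | 21 d | 28 d |
|---|---|---|---|---|
| End of infusion | −0.4 | −0.2 | −0.1 | −0.1 |
| 2 h or 8 h | 0.0 | 0.0 | 0.0 | 0.0 |
| 20 h | +0.1 | 0.0 | 0.0 | 0.0 |
| Day 5 | +0.5 | +0.1 | 0.0 | 0.0 |
| Day 7 | +1.3 | +0.3 | +0.1 | 0.0 |
| Day 14 | +11.0 | +2.9 | +1.2 | +0.6 |
| Day 28 | +22.3 | +11.0 | +5.6 | +3.3 |
| Day 56 | +7.7 | +9.9 | +7.1 | +5.0 |
| Days 14 and 56 | +18.7 | +12.8 | +8.3 | +5.6 |

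Day 56 peaks at +10.2% for a 10-day half-life. For AUCinf, Day 28 gives +22.3/+10.8/+5.3/+2.9 and Day 56 gives +7.7/+9.7/+6.7/+4.4. CL after a Day 28 loss changes by 1/1.223 − 1 = −18% down to 1/1.029 − 1 = −3%.

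**Sensitivity.** A 5.5 h infusion moves the results by about 0.2 points at most. With bi-exponential curves (50/50 with a 1.5-day, or 60/40 with a 2-day, distribution half-life; terminal half-life 7 to 28 days), Day 28 gives about +3 to +18%, Day 56 about +4 to +9%, Day 14 up to +14.5% at 7 days, and Days 5 and 7 up to +3.9%.

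**Comparison with the t_max rule.** The end-of-infusion sample is the only planned one inside the expected t_max interval (within 1 h of the end of infusion). Losing it changes AUC by 0.1 to 0.4%, and the SAP excludes the AUC. Losing Day 28 changes it by 3 to 22%, and the SAP expects no impact.

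**Do other rules catch it?** The extrapolated share in complete profiles is 0.0/1.6/6.3/12.6%, below the 20% limit, and a larger AUC0-t lowers it further. The λz rule ("At least three time points") can still be met after losing Day 28 or Day 56.

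**Reversed sign.** If Day 84 is below quantification and Day 56 is missing, AUC0-t stops at Day 28 instead of Day 56: −9.4/−23.2/−30.8/−35.2% at 7/14/21/28 days.

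**Group level, one affected subject of six.** Geometric mean: 1.03^(1/6) − 1 = +0.5% to 1.22^(1/6) − 1 = +3.4%. Power-model slope: shift = (ln d − mean ln dose)/S × ln(1 + inflation), with S = 3.704 and mean 7.505 for six subjects at each of 1000, 2000 and 3000 mg. The worst case, 22% at 1000 mg, gives (6.908 − 7.505)/3.704 × 0.199 = −0.032. The slope's 90% CI half-width is 1.746 × √(ln(1 + CV²)/3.704) = 0.18 to 0.35 for an assumed CV of 20 to 40%.

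**The case against.** The strongest reply is that little follows for the study. PK is a secondary, descriptive objective without a power calculation, and the group-level shifts are well inside the sampling error. That stands. A reader might infer that one missed visit distorts the dose-proportionality conclusion; the figures do not support it.

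A reader might also take 3 to 22% as a property of this antibody. No half-life appears in the documents, and 22% is one corner: 7 days, mono-exponential, Day 28 lost. At 14 to 28 days a single late loss costs at most about 11%. Nor is the bias always upward, as the truncation case shows. Day 14 matters little under mono-exponential decline at 14 days or more.

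It would also go too far to say that nothing is flagged. NS and NRS show the gap, and SAP 6.1.3.1 and 6.3.5 allow review of abnormal profiles and outliers. But neither names a missing sample as a trigger, the SAP has already classed this case as harmless, and the AUC, CL and Vz are unmarked. Protocol 7.2.2.4 has drug concentration measured in the ADA samples of the same visits, which could replace a lost tube; the SAP does not say it would, and it cannot help when the whole visit is missed.

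Finally, the error comes from combining wide gaps with the linear rule: linear-up/log-down gives 0.00% for a lost Day 28 or Day 56 under mono-exponential decline. That is correct, but while SAP 2.1.2 keeps the linear rule, the missing-sample sentence has to be true under it.

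**Conclusion.** The sentence is wrong as written for Days 28 and 56, and for Day 14 if the half-life is near 7 days. It conflicts with the section's own principle that timing matters, and the section is strictest where the AUC error is smallest. For an individual subject the size is about 3 to 22% (Day 28) or 4 to 10% (Day 56), conditional on a 7- to 28-day half-life, mono-exponential decline and quantifiable levels to Day 84. Bi-exponential curves give similar but somewhat narrower ranges. The consequence is confined mainly to individual AUC, CL and Vz and the ADA listing; cohort means and the power-model slope are barely affected by one such subject. The correction is worth making because it is cheap and better fixed before concentrations are disclosed.

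**What to change.** In SAP 6.1.3.1, limit the no-impact sentence to samples up to Day 7. (Days 5 and 7 are not exactly neutral, but the change is 1.3% or less in the mono-exponential case.) Then add:

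- For a missing or not reportable Day 14, 28 or 56 sample with a later quantifiable sample, interpolate the concentration log-linearly between its neighbours, for PK parameter derivation only: ln C* = ln C1 + (ln C2 − ln C1)(t − t1)/(t2 − t1). Apply the linear trapezoid as usual. Add this exception to the no-imputation rule in SAP 6.3.1.
- If no later quantifiable sample exists, send the profile to case-by-case review.
- Footnote the affected AUC, CL and Vz in the tables and in Listing 16.2.6.1, and repeat the power model without those profiles as a sensitivity analysis.
- State what happens with exactly three non-adjacent missing values, which neither existing rule covers.

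The text should say that a concentration is interpolated. A log-trapezoid over the gap alone would put the bridged AUC about 1 to 6% below the complete linear profile. Interpolating the concentration reproduces the complete profile exactly under mono-exponential decline. Applying the formula to the two bi-exponential curves above leaves about 0.4% or less for Days 28 and 56 and up to about 2.9% for Day 14.

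The cost is a few sentences in the SAP, one footnote and one sensitivity run.

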Study title	A Phase Ib, randomised, double-blind, placebo-controlled study to investigate the safety, tolerability, and pharmacokinetics of an intravenous monoclonal antibody (mAb) after single ascending doses in subjects affected by idiopathic pulmonary fibrosis
Sponsor	Chiesi Farmaceutici S.p.A. - [name]
Name of the product	CHF10067
Centre(s)	Multi-centre study (approximately 12 sites)
Indication	Idiopathic pulmonary fibrosis (IPF)
Study design	Randomised, double-blind, placebo-controlled, single-dose escalation
Study phase	Phase Ib
Objectives	
The primary objective is to assess the safety and tolerability of single ascending doses of CHF10067 in subjects with IPF.
 
The secondary objectives are:
 
• to evaluate the CHF10067 pharmacokinetic (PK) profile in serum• to evaluate the CHF10067 immunogenicity profile in terms of anti-drug antibody (ADA) and neutralising antibody (nAb). 
The exploratory objective is to evaluate transglutaminase 2 (TG2) levels in plasma.

Treatment duration	One single dose (CHF10067 or placebo)
Test product dose/route/regimen	A single 1000 mg, anticipated 2000 mg, or anticipated 3000 mg intravenous (IV) dose of CHF10067
Reference product dose/route/regimen	A single dose of placebo
Number of subjects	Twenty-four subjects will be studied in 3 cohorts (Cohort A [1000 mg], B [anticipated 2000 mg], and C [anticipated 3000 mg]) consisting of 8 subjects per cohort. In each cohort, 6 subjects will receive CHF10067, and 2 subjects will receive placebo. In each cohort, a minimum of 2 subjects are required to be not receiving antifibrotic treatment (including subjects with previous use of antifibrotic treatment that has been stopped for at least 2 weeks prior to screening).
Study population	Subjects with IPF (not receiving antifibrotic treatment [including subjects with previous use of antifibrotic treatment that has been stopped for at least 2 weeks prior to screening] or receiving standard of care treatments at a stable dose for at least 8 weeks prior to screening [nintedanib or pirfenidone].
Inclusion/exclusion criteria	Inclusion criteria: Subjects must meet all the following inclusion criteria to be eligible for enrolment into the study:

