6.2.4 Administration

No fluid or diet restrictions are required prior treatment administration.

Treatment administration must be completed within 10 hours from the removal of the product from the fridge. Doses will be administered as follows:

- Cohort A: Single doses of 1000 mg CHF10067 or placebo will be administered as an IV infusion.

Clinical Study Code No.: CLI-10067AA1-01	Version No.: 6.0
EUDRACT No.: 2022-001079-15	Date: 06 July 2023

- Cohort B: Single doses of anticipated 2000 mg CHF10067 or placebo will be administered as an IV infusion.
- Cohort C: Single doses of anticipated 3000 mg CHF10067 or placebo will be administered as an IV infusion.

The treatment administration will take place at the clinical site on Day 1 of the treatment period under the supervision of the Investigator or his/her designee. Administration will be documented in the source documents and reported in the eCRF.

Detailed instructions for administration of CHF10067 and placebo are included in the IMP Pharmacy Manual.

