12.2 Analysis Sets

Safety set: all randomised subjects who receive a dose of study treatment, including partial dose.

PK set: all subjects from the safety population excluding subjects without any valid PK measurement or with important protocol deviations significantly affecting PK, for example, use of non-permitted medications. Exact definition of important protocol deviations significantly affecting PK will be discussed by the clinical team and described in a specific

Clinical Study Code No.: CLI-10067AA1-01	Version No.: 6.0
EUDRACT No.: 2022-001079-15	Date: 06 July 2023

document before bioanalytical data are disclosed. Subjects will not be excluded on the basis of statistical analysis or for PK reasons, except in the cases defined in the European Medicine Agency guideline [24].

After unblinding, subjects will not be excluded on the basis of statistical or for PK reasons, except in the case of:

- non-zero baseline concentration $> 5\%$ of C_{\max}
- AUC_{0-t} lower than 5% of the reference medicinal product geometric mean of AUC_{0-t} (calculated without inclusion of data from the outlying subject)
- below the limit of quantification concentration at all timepoints.

Pharmacokinetic variables will be analysed in the PK set. The safety set will be used in the analysis of all safety variables. In case of deviation between randomised treatment and treatment actually received, the treatment actually received will be used (i.e., an as-treated analysis will be performed).

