6. GENERAL METHODOLOGY

6.1 ANALYSIS SETS

6.1.1 *Analysis sets*

The following analysis sets will be considered in the statistical analysis:

Enrolled Set (ENR): subjects who *signed an informed consent* to participate in this study

Randomised Set (RND): subjects who were *randomised* into this study

Safety Set (SAF): all randomised subjects who receive a dose of study treatment, including partial dose

PK Set: all subjects from the safety set excluding subjects without any valid PK measurement or with important protocol deviations significantly affecting PK, for example, use of non-permitted medications.

Notes:

- Having signed an informed consent is defined as having a complete informed consent signature date in the database.
- Randomised is defined as having a randomisation date in the database or any information to confirm randomisation.
- Having received at least one dose of study treatment is defined as having an exposure date or any information confirming exposure.
- Exact definition of important protocol deviations significantly affecting PK evaluations will be discussed by the Chiesi team during the Data Review Meeting (DRM) and described in the DRR and/or PK DRR. The PK set will be defined in the DRR and/or PK DRR. See section 6.1.3.1 for further details. Subjects will not be excluded on the basis of statistical analysis or for PK reasons, except in the cases defined in the European Medicine Agency guideline on the Investigation of Bioequivalence

Unless stated otherwise, the SAF will be used for the general characteristics, demographics and baseline characteristics, immunogenicity and safety tables and figures and the RND will be used for the general characteristics and safety listings. In addition, the PK set will be used for demographics and baseline characteristics tables, if different than the SAF. PK set will be used for the PK tables, listings and figures.

6.1.2 *As planned versus as actual analysis*

For the safety, immunogenicity, other variables (TG2) and PK analyses the actual treatment of the subject will be considered. The general characteristics analyses will be by planned treatment. In the listings the actual treatment will be presented.

6.1.3 *Exclusion of data from the statistical analyses*

The important/non-important protocol deviation definitions are defined in the Protocol Deviation Criteria List and will be used to identify cases that will be

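### SAP 6.1.3.1 removes the whole subject from the PK set when AUC0-t is very low, so a fully dosed subject with no sample from Day 5 onward can also lose a valid Cmax

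*SAP*

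**What the plan says.** SAP 6.1.3.1, under the rules that apply after the bioanalytical data are disclosed, compares each subject's AUC0-t with 5% of the *corresponding* geometric mean. A subject below it is removed: "calculated without inclusion of data from the outlying subject) will be excluded from the PK set". The SAP describes these rules as "in line with the EMA guideline on the investigation of bioequivalence CPMP/EWP/QWP/1401/98 Rev.1 2010". No condition is set on why AUC0-t is low, and *corresponding* is not defined.

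Protocol 12.2 already lists the same criterion, but as a permitted exception to a ban on exclusion, and with a different comparator: "lower than 5% of the reference medicinal product geometric mean". The reference product in the protocol outline is "A single dose of placebo", so that comparator does not exist here. SAP 7.1 does not list the substitution.

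Removal reaches every PK output, because "PK set will be used for the PK tables, listings and figures" (SAP 6.1.1). AUC0-t is "AUC from 0 to the last quantifiable concentration", while Cmax and tmax "will be obtained directly from the experimental data without interpolation" (both SAP 2.1.2). SAP 6.1.3.1 expects tmax within 1 hour of the end of infusion.

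**The concern.** AUC0-t measures length of follow-up as well as exposure. A subject with normal exposure who leaves soon after dosing has a small AUC0-t compared with subjects sampled to Day 84, yet may have a perfectly good end-of-infusion sample. The rule then discards concentrations, Cmax, tmax and Cinf because of a defect that touches only the AUC.

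The rule is also not needed to detect a missed dose. The infusion is given on site "under the supervision of the Investigator or his/her designee" (Protocol 6.2.4), and SAP 5.6.1 records dose, infusion rate and interruptions. The cause of a low AUC0-t can be looked up.

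The rule sits oddly with the rest of the SAP, which excludes by parameter or time point. Extrapolation above 20% drops only AUCinf, CL and Vz (2.1.2). A missed tinf sample drops only Cinf (6.1.3.1). A deviation at one time point removes only the data affected (6.1.3).

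At stake is a Cmax value in a dose group of six, for a secondary objective. Discontinuations for drug-related safety reasons are not replaced (Protocol 4.4), so that value could not be made up. Listing 16.2.5.2 covers the PK set only, so the excluded concentrations might not be listed either, although Protocol 12.3.1 calls for all individual concentrations to be listed.

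**Working it through.** The plan gives no figure to reproduce. The documents (as released) give no half-life, variability or infusion duration, so these are assumptions shown over a range.

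**1. Can short follow-up alone trip the rule?**

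Inputs from the documents: samples at the end of infusion, 2, 4, 8 and 20 h after it, and Days 5, 7, 14, 28, 56 and 84 (SAP 2.1.1), with target times from SAP 6.2.4; linear trapezoidal AUC (SAP 2.1.2). Assumed: one-compartment decline, 3 h infusion, comparators sampled to Day 84, and a leaver with the same kinetics as they have.

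Formula: C(t) = C_EOI × exp(−k(t − T)), k = ln 2 / half-life, T = end of infusion. Ratio = trapezoidal AUC to the last sample ÷ trapezoidal AUC to Day 84.

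Example, half-life 14 days, C_EOI = 1, in days: the infusion contributes 0.125/2 = 0.0625; the 20 h after it contribute 0.816; the total to 20 h is 0.879. The total to Day 84 is 20.96. Ratio = 0.879/20.96 = 4.2%.

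| Half-life (days) | Last sample 8 h | Last sample 20 h | Last sample Day 5 |
|---|---|---|---|
| 7 | 3.5% | 7.8% | 30.7% |
| 10 | 2.5% | 5.6% | 23.1% |
| 14 | 1.9% | 4.2% | 17.6% |
| 21 | 1.3% | 3.0% | 13.0% |
| 28 | 1.1% | 2.5% | 10.8% |

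At 20 h the ratio crosses 5% at a half-life of 10.9, 11.4 or 12.2 days for infusions of 1, 3 or 5.5 h.

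Two two-compartment profiles, with infusions of 1 and 5.5 h, give a milder picture. (CL 0.25 L/day and Q 0.5 L/day, or CL 0.5 and Q 0.6; both volumes 3 L; terminal half-life about 19 and 10 days.) The ratios are 2.8% to 6.3% at 8 h, 6.4% to 12.4% at 20 h and 23.2% to 37.8% at Day 5. The 8 h leaver is caught in one profile and kept in the other; the 20 h leaver is kept in both.

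**2. Would ordinary variability trip it?**

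For a complete lognormal profile compared with the geometric mean of the five others at its dose level: P = Φ( ln 0.05 / (s√(1 + 1/5)) ), s = √ln(1 + CV²).

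- CV 30%: s = 0.294, z = −9.32, P ≈ 6×10⁻²¹.
- CV 50%: s = 0.472, z = −5.79, P ≈ 4×10⁻⁹.
- CV 100%: s = 0.833, z = −3.28, P ≈ 5×10⁻⁴; for any of 18 active subjects, 1 − (1 − 0.00051)^18 ≈ 0.9%.

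**3. What does one lost Cmax cost?**

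The standard error of a dose-level log mean grows by √(6/5) = 1.095, about 10%. For the power-model slope, Sxx = 6 × Σ(ln dose − mean)² = 3.70. At CV 30% the 90% CI half-width is t(0.95, 16) × s/√Sxx = 1.746 × 0.294/1.924 = 0.27. With 17 subjects it is 0.27 to 0.28, depending on the dose level that loses one.

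**4. Why an incomplete infusion is a different case**

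The code in SAP 10.1 regresses on nominal dose. Take one Cmax at 5% of its peers, entered at nominal dose. It multiplies the geometric mean of six by 0.05^(1/6) = 0.61, a fall of 39%. It shifts the slope by ln 0.05 × (ln dose − mean)/Sxx:

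- 3000 mg: −2.996 × 0.501/3.70 = −0.41
- 1000 mg: −2.996 × (−0.597)/3.70 = +0.48

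Either shift exceeds the 0.27 half-width at CV 30%.

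**The case against.** The strongest objection is that the 5% rule may never reach an early leaver. SAP 6.1.3.1 refers to a schema for AUCs when the last planned sample is not performed, and that figure is not shown in the text available. If it makes AUC0-t non-estimable, there is nothing to compare. This stands as a real uncertainty; no visible text switches off the exclusion.

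Protocol 7.2.2.4 also has antibody samples, including those at early termination, assayed for drug concentration. If such a value enters the profile, AUC0-t runs later. The documents do not say whether it does.

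The rule is objective and pre-specified in Protocol 12.2. Exclusions and reasons are listed (SAP 2.1.4; Listing 16.2.5.3), so nothing is hidden. Other leavers before Day 14 are replaced, which limits the loss to drug-related safety discontinuations. Adapting an inapplicable reference-product comparator is sensible; its absence from SAP 7.1 is clerical.

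A reader might infer more: that early leavers in general lose their Cmax, that anyone leaving on Day 1 or 2 fails, or that genuinely low exposures are deleted and dose-level exposure is biased upward. The figures do not support this. A sample from Day 5 onward protects the subject, a 20 h sample often does, and a complete, fully dosed profile practically never falls below 5%. Retaining every flagged subject would also be wrong, since a nearly aborted infusion would distort a model fitted to nominal dose.

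**Conclusion.** The concern holds in a narrow form. As written, SAP 6.1.3.1 removes a whole subject because of one parameter, whatever the cause, against an undefined comparator. If AUC0-t is calculated for a fully dosed subject whose last quantifiable sample is at 8 h, or at 20 h with a half-life of about 12 days or more, truncated follow-up alone can trip the rule and valid data are lost. The half-life threshold rests on the one-compartment assumption; with a marked distribution phase fewer subjects are caught.

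The size is small: at most a rare subject, one of six Cmax values at a dose level, and almost no change in slope precision. No bias claim follows. The reason to act is that a stated rule would discard valid observations when it fires, and the wording is easy to repair. It is a point to consider.

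**What to change.** In SAP 6.1.3.1, before the bioanalytical data are disclosed:

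- State that *corresponding* means the same dose level.
- Where AUC0-t is below 5% because sampling was truncated after a full dose, exclude only AUC0-t. AUCinf, CL and Vz follow Section 2.1.2. Keep the subject in the PK set with concentrations, Cmax, tmax and Cinf, provided the end-of-infusion sample is valid.
- Where an incomplete infusion meets the 5% criterion, keep the existing exclusion from the main analysis, because the power model uses nominal dose, but list the values.
- Rerun both the dose-level summary and the power model with any excluded subject included, as a sensitivity analysis.
- Record the departure from Protocol 12.2 in SAP 7.1, noting that its reference product is placebo here.

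The cost is a few lines of SAP text and one extra sensitivity run. No new data are needed.
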